3.1.1. Overall Study Design

This is a Phase 1, open-label, study to evaluate the safety, tolerability, PK, PD, and preliminary clinical activity of single ascending doses of SBT777101 in patients with active RA.

Following screening, eligible subjects will undergo apheresis, and SBT777101 drug product will be manufactured for each subject. Each subject will receive a single dose of SBT777101 intravenously (IV) on study Day 1. Subject safety will be monitored acutely post dosing and throughout the study for 1 year. After one year and due to the use of lentivirus vector in SBT777101, all subjects will be encouraged to participate in a long-term safety follow-up (observational) study that will be conducted under a separate protocol in accordance with current FDA guidance.

The overall study design is displayed in Figure 1. A schedule of assessments (SoA) is provided in Appendix A and Appendix B.

Figure 1: Study Design

Dose Escalation Cohorts

The study will be open-label and employ a "3+3 Dose Escalation" design. Initially three eligible subjects will be evaluated in each cohort, enrolled for a safety monitoring period at least 14 days apart. Subjects will be monitored for dose limiting toxicities (DLTs) for at least 28 days following enrollment of the third or sixth subject.

- If a DLT is not seen in the first three subjects, then escalation to the next dose level may occur.
- If a DLT is seen in 1 of the first 3 subjects in any dose cohort, the cohort size will be expanded to six subjects. These additional subjects will be dosed at least 14 days apart and have a safety monitoring period of at least 28 days.
- If more than one DLT occurs in ≤6 subjects in a dose cohort, dose escalation will not occur, and this dose level will be identified as the non-tolerated dose. Otherwise, dose escalation may occur.

See Section 3.3 for definitions of DLTs and details of dose escalation rules.

Additional subjects may be screened and undergo apheresis at risk prior to the previous subject within a dose escalation cohort being dosed or completing their post dose safety monitoring period. These additional subjects will not receive treatment with SBT777101 until the safety monitoring period has been completed for the prior subject.

Dose escalation will be overseen by the study Safety Monitoring Committee (SMC; see Section 3.3).

Backfill Cohorts

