At the Sponsor's discretion, additional eligible subjects (e.g., those beyond the initial 3 or 6 subjects initially treated as described above) may be enrolled into optional protocol-defined dose level "backfill" cohorts. Each backfill cohort will contain up to six subjects dosed at least 14 days apart. Backfill cohorts will not be opened until the dose escalation cohort at that dose level has been completed. Doses will not exceed the last cleared dose from the initial dose escalation cohorts.

Additional subjects may be enrolled at the Sponsor's discretion under the following conditions:

[figure not shown]

- Inability to manufacture the required dose of SBT777101 for any given subject, wherein the number of CAR positive T_{reg} cells is in the final drug product is insufficient for the assigned dose level. In this case, the subject may be enrolled into a backfill cohort at the highest possible cleared dose level (e.g., a subject intended for dose level 2 may be enrolled in dose level 1 backfill).
- Evaluation of PK, PD and biomarker data from a dose cohort indicates that additional data may better aid interpretation of preliminary PK and PD data and to guide future dose selection. Subjects may be added provided that the SMC does not indicate that doing so will present additional safety risks.

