3.1.3. Starting dose and dose levels

Eligible subjects will be enrolled into sequential dose-level cohorts and will receive a single dose of SBT777101 by IV administration. Planned dose levels are shown in Table 1. Selection of dose levels for cohorts 2 and 3 will be overseen by the SMC in collaboration with the Sponsor.

Table 1: Planned Dosed During Dose Escalation

Planned dose	Total CAR ⁺ T cells (noted by EGFR expression)
1 (Starting dose)	100 x 10 ⁶
2	300×10^6
3 (Maximum dose)	900 x 10 ⁶

If a dose limiting safety event is observed the Sponsor may choose to enroll subjects into a cohort at a dose lower than 100×10^6 cells. Dose selection and initiation of this cohort would be overseen by the SMC.

Although three dose level cohorts are planned, fewer or additional cohorts may be included based on safety observations and/or study product manufacturing limitations. These additional dose levels will be lower than the maximum planned dose of 900×10^6 transduced cells. Determination of dose levels for additional cohorts will be overseen by the SMC in collaboration with the Sponsor.

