3.3. Dose Escalation Rules

Determination of dosing within a cohort will be overseen by the SMC. Dosing may be temporarily withheld, modified (expansion of cohort size from three to six subjects) or stopped (with no further subject enrollment into the cohort) if any event or series of events occurs that suggests that there is a significant safety risk to subjects, or a clinically significant pattern of toxicity occurs in several subjects.

Dose-Limiting Toxicity Definition

A dose-limiting toxicity (DLT) is defined as any treatment-emergent CTCAE \geq Grade 3 AE considered related to study drug, except Grade 3 infusion reactions that are rapidly reversible with supportive care and that do not recur following re-initiation of the study drug infusion.

If 1 of the first 3 subjects experiences a DLT during the first 28 days after SBT777101 administration, an additional three subjects will be enrolled into the cohort, for a total of 6 subjects. Subjects who discontinue from the study prior to Week 4 for reasons unrelated to study treatment will be considered non-evaluable for dose escalation decisions and will be replaced with another subject at that same dose (see Section 7.4.3).

If 0 of 3 or \leq 1 of 6 subjects experience a DLT during the 28-day DLT evaluation period, and cumulative safety data support tolerability of the dose level as determined by the SMC, escalation to the next higher dose level will be initiated. If \geq 2 subjects in a cohort experience a DLT during the first 28 days or if cumulative safety data suggest an overall unacceptable toxicity profile, dose escalation will be discontinued and either the prior dose level will be considered the maximum tolerated dose (MTD) or an intermediate dose level will be evaluated.

In addition, dose escalation will be temporarily halted if any of the following occur:

- One subject in a cohort experiences a potentially life-threatening AE considered related to study drug
- Two or more subjects experience similar SAEs considered related to study drug

The SMC review of safety data will serve as the basis on which the Sponsor will determine whether dosing can be resumed. Further details may be found in the SMC Charter.

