3.4. Safety Monitoring Committee

An SMC will regularly assess the safety of SBT777101. The SMC will provide their assessment of safety and recommendations for dose escalation and ongoing study conduct (see SMC Charter for further details).

The SMC will consist of at least the Principal Investigators, the Sponsor's Medical Monitor, an independent physician with expertise in RA, and an independent physician with expertise in CAR T therapy. Dose escalation decisions will be made by the SMC in collaboration with the study Investigators.

The SMC will convene approximately four weeks after the first subject has been dosed in each dose escalation cohort. They will then reconvene on a regular basis during the study to review available clinical study data or on an ad hoc basis if a DLT occurs.

Based on ongoing assessment of benefit and risk, the SMC may recommend dose escalation, stop dose escalation before the maximum proposed dose is reached or stop dosing completely.

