7.1.2.4. Pre-Infusion Eligibility Confirmation

Subject eligibility must be reconfirmed between study Days -10 and -4 to confirm that it is safe and appropriate that the subject receives study drug.

If any of the eligibility criteria are not met the subject must not be dosed with SBT777101. In this case, the subject remains enrolled but will need to be reassessed according to the pre-infusion eligibility criteria before dosing. Subjects can be reassessed for up to 6 months after enrollment. A subject that is not dosed within 6 months of being enrolled will be withdrawn from the study. A second apheresis is not required for subjects who qualify for infusion upon reassessment and have an available SBT777101 cell product that met the release criteria.

Subjects with active infections during the pre-treatment period should not be dosed until at least four weeks after completion of IV antibiotics and two weeks after completion of treatment with oral antibiotics/anti-infectives.

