8. ASSESSMENT OF SAFETY

8.1. Safety Plan

This is the first study in which SBT777101 will be administered to humans. As such, the actual risks are unknown. The anticipated potential and theoretical safety risks for subjects are detailed in the sections below. Please refer to the Investigator Brochure for SBT777101 for a complete summary of safety information.

Measures will be taken to ensure the safety of subjects participating in this study, including the use of stringent inclusion and exclusion criteria (see Section 4), and rigorous monitoring

assessments as detailed in Section 8.1.1. As described in Section 3.1.1, all subjects receiving SBT777101 in dose escalation cohorts will be dosed at least 14 days apart and monitored for onset of DLTs for at least 28 days prior to dose escalation. In addition, subjects in backfill cohorts will be dosed 14 days apart. Dosing of subsequent subjects within cohorts and dose escalation decisions will be made by a SMC in collaboration with the study Investigators (see Section 3.3).

All subjects will be monitored closely for toxicity. Administration of SBT777101 will be performed in a setting with available emergency medical facilities and staff who are trained to monitor for and respond to medical emergencies. Subjects will be closely monitored for acute safety events at the site under direct supervision of medical staff post administration of study drug. Safety monitoring should be performed as described below:

- Subjects should remain in a supine or semi-reclined position prior to and for the duration of the infusion. Vital signs must be measured approximately 15 minutes prior to infusion, and approximately every 15 minutes during the infusion.
- Subjects must remain at the study site/medical facility under medical supervision for at least 24 hours from the start of the Day 1 study drug infusion through completion of procedures at the Day 2 study visit.
- Subjects will be contacted by study staff on Days 3-7 to check for adverse events and provide reminders for temperature monitoring. Check-in may occur by phone call, text, or other method.
- The Sponsor recommends the following from study Day 2 to Day 28:
 - Subjects should stay within approximately 1 hour travel time to the study site from Day 2 through completion of procedures at the Day 7 study visit.
 - The subject remains under the care of a responsible adult in case of the onset of unexpected adverse medical events

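### The automatic safety rules in Protocol 3.3 stop dose escalation, not dosing, so read literally they do not pause backfill infusions at a cleared level

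*Protocol*

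**What the plan says.** Protocol 3.3 gives two halt triggers, introduced by "In addition, dose escalation will be temporarily halted if any of the following occur": a drug-related, potentially life-threatening AE in one subject of a cohort, and similar drug-related SAEs in two or more subjects. The next sentence reads "The SMC review of safety data will serve as the basis on which the Sponsor will determine whether dosing can be resumed". The DLT rule in 3.3 says that two or more subjects with a DLT in a cohort within 28 days end escalation; the prior dose then becomes the MTD, or an intermediate dose is tested. The matching bullet in 3.1.1 stands under Dose Escalation Cohorts and says that on more than one DLT "dose escalation will not occur, and this dose level will be identified as the non-tolerated dose".

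Backfill is described separately in 3.1.1. It opens only after the escalation cohort at that level is complete, takes up to six subjects per level at least 14 days apart, and has a dose ceiling: "Doses will not exceed the last cleared dose from the initial dose escalation cohorts". On any extra levels, 3.1.3 says "These additional dose levels will be lower than the maximum planned dose of" 900 x 10^6 cells, so nothing lies above that dose. Section 8.1 says that "subjects receiving SBT777101 in dose escalation cohorts will be dosed at least 14 days apart and monitored for onset of DLTs"; the minimum window there is 28 days before escalation. For backfill it gives only the 14-day spacing.

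**The concern.** A rule that halts escalation protects the next dose level. Backfill subjects are infused at the current level or a lower one. If a backfill subject has a related life-threatening event, the written automatic action blocks a step up but does not say that the next backfill subject at the same dose must wait. At the maximum dose there is no step up left to block.

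This matters because backfill may supply half of the study (18 of 36 subjects). A level may have been cleared on 0 DLTs in 3 subjects, after which a full backfill is 6 of the 9 subjects at that dose. The product is first-in-human and is given as a single infusion. Sites should be able to read from the protocol which infusions stop on the day an event occurs.

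**Working it through.** **1. The plan's own count.** Three levels x 3 = 9 subjects at minimum. Three levels x 6 = 18 in escalation, plus three levels x 6 = 18 in backfill, gives 36. This reproduces the 9 to 36 in the Synopsis and the 18 + 18 in 9.1. The protocol states no DLT rate and no operating characteristic.

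**2. What each automatic rule stops.**

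| Rule | Stated action | Backfill infusions at that dose |
|---|---|---|
| More than one DLT in up to six subjects (3.1.1) | No escalation; level labelled non-tolerated | Not mentioned; bullet sits under escalation cohorts |
| Two or more subjects with a DLT in a cohort (3.3) | Escalation ends; prior dose is the MTD, or an intermediate dose is tested | Not mentioned |
| One related, potentially life-threatening AE (3.3) | Escalation halted temporarily | Not mentioned |
| Two or more subjects with similar related SAEs (3.3) | Escalation halted temporarily | Not mentioned |
| Resumption sentence (3.3) | Sponsor decides whether dosing resumes | Implies that dosing had stopped |

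A backfill event at 100 or 300 x 10^6 can therefore halt escalation above it while same-dose infusions are left to inference. At 900 x 10^6 the stated action stops no infusion. Relabelling the MTD does not clearly close backfill either, because the backfill ceiling is tied to the doses cleared in the initial escalation cohorts.

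**3. How often the unaddressed situation could arise.** Assumptions: true DLT rate p (a range, since the protocol gives none), independent subjects, a full backfill of six, and no SMC action.

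- Level clears 3+3: P(clear) = (1-p)^3 + 3p(1-p)^2 x (1-p)^3.
- Two or more DLTs in six backfill subjects: P2 = 1 - (1-p)^6 - 6p(1-p)^5.
- Both: P(clear) x P2.
- Mean number dosed after the second backfill DLT if nothing stops: sum over j = 2 to 6 of (j-1) p^2 (1-p)^(j-2) (6-j). This averages over all full backfills and takes each outcome as known before the next dose.

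| p | P(clear) | P2 | Both | Mean dosed after second DLT |
|---|---|---|---|---|
| 0.05 | 0.973 | 0.033 | 0.032 | 0.05 |
| 0.10 | 0.906 | 0.114 | 0.104 | 0.17 |
| 0.20 | 0.709 | 0.345 | 0.244 | 0.59 |
| 0.30 | 0.494 | 0.580 | 0.287 | 1.13 |
| 0.40 | 0.309 | 0.767 | 0.237 | 1.70 |

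Example at p = 0.30: P(clear) = 0.343 + 0.151 = 0.494; P2 = 1 - 0.118 - 0.303 = 0.580 (unrounded terms); product 0.287.

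The last column is an upper limit on infusions avoided. With 14-day spacing, the next subject can be dosed halfway through the previous subject's 28-day window, before a late DLT is known. The two AE/SAE triggers cannot be quantified because the protocol gives no rates for them.

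**The case against.** The strongest reply is that the SMC already controls backfill dosing. The opening paragraph of 3.3 concerns dosing, not escalation: the SMC oversees it within a cohort, and it may be withheld or stopped on any significant safety signal, with no limit to escalation cohorts. Under 3.4 the SMC meets regularly to "review available clinical study data or on an ad hoc basis if a DLT occurs", and may stop dosing altogether. Section 3.5 pauses the study once the SMC finds an AE pattern that raises risk for subjects already enrolled. Section 8.1 makes dosing of each subsequent subject within a cohort an SMC decision, and 3.1.1 gives the SMC a veto over backfill added for PK/PD reasons. The DLT definition has no cohort restriction, a cohort in 3.3 may include a backfill cohort, and the resumption sentence suggests that dosing was meant to stop. The SMC Charter, cited but not shown, may say more, and so may Figure 2, which is also not shown.

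All of this stands. A reader might infer that backfill subjects are unprotected, or that infusions would continue after a life-threatening event. The documents do not support that. What remains is narrower: each of these safeguards needs a committee judgement first, and none is an automatic pause between the event and the review, which 3.3 does set for escalation.

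A reader might also infer that the plan needs a numerical boundary on pooled escalation and backfill DLTs, for example a hold at a pooled rate of one third. The arithmetic does not support that. From 0 of 3 or from 1 of 6, such a boundary needs two DLTs in the first three backfill subjects or three in six, so it fires only when the backfill cohort already has at least two. At p = 0.30, checked after each subject, it would hold 32.1% of cleared levels, against 58.0% for the existing two-DLT threshold applied to the backfill cohort. It also misses two DLTs when the second falls at backfill subject 4, 5 or 6.

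**Conclusion.** The concern holds as a defect of wording and scope. The three automatic rules in 3.3 name escalation as the thing that stops, while the following sentence presumes that dosing stopped. On the literal reading backfill at a cleared level is not paused, and at the maximum dose the rules stop no infusion. Backfill then depends on SMC judgement alone.

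The conclusion rests on the text and not on any DLT rate. The figures only show that the situation is not remote: about 10% of levels at an assumed 10% DLT rate, and 24% to 29% at 20% to 40%, if the optional backfill is filled. The infusions at stake are few, on average 0.6 to 1.7 per full backfill at rates of 20% to 40%, and fewer if the SMC acts or outcomes are known late. It is still worth fixing, because the correction is cheap and removes a doubt about which infusions stop. The SMC Charter may already settle part of it.

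**What to change.** 1. In 3.3, reword both halt triggers and the consequence of two or more DLTs so that dosing at that level and above, backfill included, pauses pending SMC review. State that a cohort includes a backfill cohort, and keep the 3.1.1 bullet consistent.
2. In 3.1.1 and 8.1, state that backfill subjects have the same 28-day DLT evaluation. Appendix B gives one visit schedule for all subjects, so no visits are added.

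At most, ask the SMC also to review cumulative DLTs by dose level. A pooled numerical boundary is not needed.

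The cost is wording in the protocol and the SMC Charter, with no extra subjects. The downside is an occasional pause. Under the two-DLT rule this would affect about 3% / 11% / 34% of full backfills at true DLT rates of 5% / 10% / 20%; the AE and SAE triggers would add pauses that cannot be quantified. A pause could push a subject who has already had apheresis towards the limit in 7.1.2.4: "A subject that is not dosed within 6 months of being enrolled will be withdrawn from the study". The SMC review should therefore be prompt.

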3.4. Safety Monitoring Committee

An SMC will regularly assess the safety of SBT777101. The SMC will provide their assessment of safety and recommendations for dose escalation and ongoing study conduct (see SMC Charter for further details).

The SMC will consist of at least the Principal Investigators, the Sponsor's Medical Monitor, an independent physician with expertise in RA, and an independent physician with expertise in CAR T therapy. Dose escalation decisions will be made by the SMC in collaboration with the study Investigators.

The SMC will convene approximately four weeks after the first subject has been dosed in each dose escalation cohort. They will then reconvene on a regular basis during the study to review available clinical study data or on an ad hoc basis if a DLT occurs.

Based on ongoing assessment of benefit and risk, the SMC may recommend dose escalation, stop dose escalation before the maximum proposed dose is reached or stop dosing completely.

3.5. Study Stopping Rules

The study will be paused, and the risk to other subjects evaluated, prior to a decision as to whether to terminate the study if any of the following criteria are met:

- A decision to stop dose escalation or study activities has been recommended by the SMC in two cohorts for safety concerns
- The SMC determines that a pattern of adverse events would preclude evaluation of any further dose cohorts or place subjects already in the study at increased safety risk

Alternatively, the SMC may determine that dose escalation may be delayed, paused, or modified as deemed appropriate.

3.6. End of Study Definition

Up to 36 eligible adult subjects will be enrolled in the study; up to 18 subjects will be enrolled in dose escalation cohorts and an additional 18 subjects may be included in optional backfill cohorts. Each subject will participate in the study for approximately 15 months. The study duration is expected to be approximately 24 months.

A subject is considered to have completed the study if they have completed all periods of the study including the final safety follow-up or early termination visit.

The end of the study is defined as the date of the last visit of the last subject in the study.

In addition, the Sponsor may decide to terminate the study at any time.

All subjects that receive SBT777101 will be encouraged to participate in a long-term follow-up trial under a separate protocol.

4. STUDY POPULATION

4.1. Inclusion Criteria

All subjects must meet all of the following inclusion criteria:

- 1. Age ≥ 18 and ≤ 70 at the time of signing the informed consent
- 2. Body mass index (BMI) <35 kg/m², inclusive

RA Characteristics

- 3. Diagnosis of adult-onset RA as defined by the 2010 ACR/EULAR classification criteria for RA
- 4. Moderate-to-severe active disease defined by DAS28 >3.1 (calculated using CRP)
- 5. Must have at least one joint that can be used for synovial biopsy
- 6. Clinical and/or ultrasound evidence of synovitis
- 7. Have had an inadequate response to prior treatment with available therapies, including at least two prior treatment options with differing mechanisms of action
 - Prior treatment options include approved therapies or biosimilars that target TNF (e.g., adalimumab, golimumab, etanercept, infliximab), IL-6 (e.g., tocilizumab, sarilumab), IL-1 (e.g., anakinra), T cells (e.g., abatacept), CD20 (e.g., rituximab), or JAK (e.g., baricitinib, filgotinib, tofacitinib)
- 8. Doses of medications for RA (or biosimilar equivalents) including methotrexate, hydroxychloroquine, adalimumab, golimumab, infliximab, certolizumab, etanercept, anakinra, tocilizumab or sarilumab must be stable for 30 days prior to the screening visit

Contraceptive/Barrier Requirements

9. Women of childbearing potential must agree to use two methods of contraceptive for at least one year post SBT777101 administration. One method must be considered a highly effective

method of contraception, while the second method may be a barrier method (refer to Appendix D).

- 10. Women of childbearing potential must have a negative urine pregnancy test before the administration of study drug performed on the day of study drug administration
- 11. Males who are sexually active with women of childbearing potential must agree to use one method of contraception for one year post SBT777101 administration (refer to Appendix D).
- 12. Male subjects must refrain from donating sperm for one year post SBT777101 administration

Other Inclusions

- 13. Ability to comply with all the requirements of the study, in the Investigator's opinion
- 14. Adequate vascular access, in the opinion of the Investigator, for apheresis procedure
- 15. Willing to undergo repeat synovial biopsies to obtain tissue and synovial fluid collections during the study
- 16. Willing to comply with study specific safety monitoring requirements (see Section 8.1)
- 17. Willing and able to provide signed informed consent

